The patient will then be sent a consent packet that contains a cover letter from the program, a program brochure, a copy of the program eligibility criteria, two copies of the consent and authorization form (one to sign and return and one to keep), an information sheet on CGM, a Fitbit sizing guide, and a program survey.

If a patient is invited to study during a clinic visit and wishes to learn more, the patient may also meet and discuss the study with the clinical research coordinator (CRC), and receive a consent packet at that time.

---

 Inclusion/exclusion criteria have been determined by [name] and [name], Co-Investigators and Senior Medical Directors at SMA.

COMPLETION	
 
Patient completes survey.
 
Patient keeps the smartphone and tracker if patient has continued to track and sync steps through end of study period.
 

EDUCATION	
 
Patient wears CGM system for 10 weeks.
 
Patient is encouraged to wear activity tracker throughout end of study.
 
Throughout the study, patient will receive a weekly call from patient's coach.
 
Coach will be available to patient via phone and text through duration of study.
 
Patient may request CGM summary data to-date at any time during study.
 

SET-UP	
 
Patients have option to start using CGM on their own at home or at a group visit at the study site. If needed the CRC will assist patients with set-up at home.
 
Patients choosing home set-up on their own will receive devices in the mail. Patients choosing the group visit will receive devices during the visit.
 
During and after CGM initial set-up, the patient will have access to the CGM system Quick Start Guide, instructional videos, instructional booklet, and guidance from Dexcom technical support, program staff, the CRC, and/or a coach.
 
Patients will receive activity tracker instruction and support from coach when patients feel they are ready to start tracking activity.
 

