#### [CGM-based education and coaching](#)

This part of the study will be implemented by coaches who have undergone diabetes management training that incorporates device information, educational content, and techniques based on behavioral discussion and patient self-learning/empowerment. Coaches will also be equipped to help patients use

activity data in conjunction with their CGM use. Coaches will receive training regarding human research subjects to insure the ethical treatment and safety of all participants. All training will be reinforced during contact with study staff.

The information contained in the Standard of Care document has been approved by the study's Medical Directors (co-investigators) as providing fundamental diabetes self-management information to patients with T2D. In the Standard of Care document, patients are instructed that this information does not replace individual guidance given to patients from their providers.

Each participant will be assigned a coach who will provide education and support via phone and secure text messaging throughout the course of the study. Education will be centered around the four educational objectives (food intake and PPG, walking to reduce PPG, medication adherence, and nighttime glucose monitoring) and reinforcement of messages in the patient standard of care document. The coach will provide education on how to optimally use the CGM system for self-discovery, focusing on effective times to look at the CGM and behaviors that are likely to impact the CGM (outlined above). Coaches will assist participants in setting personalized goals and act as a sounding board for participants to discuss their self-discoveries. Coaches will review with patients the Rule of 15 to deal with hypoglycemic episodes.

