#### [Integration with patient care](#)

Throughout the program, patients will be instructed to follow their normal care plan as directed by their medical providers and as consistent with ADA 2017 standard-of-care guidelines. This includes taking medications as prescribed; engaging in physical activity—especially walking after meals; eating a diet that optimizes glucose control through food choice and timing; responding to hypoglycemia symptoms with a fingerstick and consuming a pre-determined amount of glucose; and monitoring emotional wellness. By providing a continuous graph of each participant's glucose, the CGM system illustrates how the above-described glucose management behaviors impact the participant's glucose.

Should patients in the course of the program experience any health problems associated with the use of their CGM devices, they will be directed to contact the study doctor's CRC. The CRC will assess the severity and relatedness of the event and arrange for appropriate care. Should patients mention a potential study-related health concern to their coach, the coach will actively work to assure the patient speaks with the study doctor, either through a warm transfer or callback.

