### Patient Participation

All program participants will participate at-will and have the freedom to terminate their participation at any time. Participants, including those who intend to withdraw from the program or those who have withdrawn will be able to access program coaches for assistance with any program-related questions or issues.

Coaches will schedule weekly calls with participating patients. If patients demonstrate by their actions that they no longer want to participate in the study by no longer syncing their CGM or activity tracker data, outbound call or text messaging efforts will be made to reach the patient. If after three weeks there has been no data received and no communication with the patient, a voicemail will be left asking patients to reply within three days or they will be considered dropped from the study. No response to these voicemails will result in the shipment to these patients of a postage-paid box and a letter. The letter will inform patients that they are considered as non-participating and need to return the CGM devices, activity tracker, and smartphone.

During the course of the program, should any participant report medical issues that may affect that patient's ability to participate in the program, the patient will be directed to consult with the study doctor.

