- There are no expected electrical safety risks as the device has passed the electrical safety tests as per EN45502-1 and EN60601;

- If the subject feels any discomfort during the course of the study, he/she will be able to remove the device immediately (the device is not permanent);
- The device is being used to complement, not replace, self-monitoring of blood glucose meter information, and readings are not intended to be used alone to make diabetes self-management decisions. As with the currently approved device and per intended use of similar technologies, subjects in the study will be instructed not to use the device for diabetes therapy or management;
- Subjects will be instructed to monitor their blood glucose levels as per their usual practice.

Adverse events (AE) associated with the use of the device include pruritus (severe itchiness present 48 hours after removal), erythema (reddening of the skin present 48 hours after removal), and inflammation (swelling and pain, defined as 8 or greater on a 10 point scale 48 hours after removal) where the adhesive touches the skin; local infection at insertion site; and shooting pain located at the site of the sensor (defined as 8 or greater on a 10 point scale). Rarely, the sensor wire will fracture when the sensor is being inserted, worn, or removed. If a sensor breaks and no portion of it is visible above the skin, the participant will be instructed to not remove it and seek medical care from the study doctor and/or his staff.

No serious adverse events (SAE) are expected as a result of participation in this minimal risk study. However, AE and SAE will be monitored in the following ways:

- Participants in the study will be instructed to call the study doctor's clinical research coordinator to report all AE and SAE related to the use of the study devices. The study doctor and/or his staff will assess the severity of any health problems associated with the device, and if needed, see the patient at the study clinic to assure appropriate care.
- Study coaches will listen for any reports of AE or SAE in the course of their communications with participants, and will connect reporting patients with the study doctor's clinical research coordinator so events can be assessed and documented and patients can receive care, if needed.

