## 22. Appendix B

### Adverse Events Severity and Relatedness Questions

May 2017

When patients share a complaint, program coaches will identify the complaint in the Anticipated Complaints Guidebook. Based on the complaint type, coaches will then ask questions to determine:

1. Severity of the complaint (e.g., Mild, Moderate, or Severe), and
2. Relatedness of the complaint to the use of program devices (e.g., Not Related, Probably Not Related, Possibly Related, and Probably Related)

Coaches will document answers in the templates provided, including the Adverse Event document.

If the complaint falls in any of the severity categories highlighted in red, the coach will make a “warm transfer” to the study doctor and/or his staff so that the patient can be scheduled for an ancillary appointment.

If the complaint is an emergency, patients will be instructed to call 911.

If a patient has a complaint that is not listed in the Anticipated Complaints Guidebook, the coach can “warm transfer” the patient to the study clinic for guidance. The coach will document as much as possible in Adverse Event document. Follow up with the clinic will determine severity and relatedness.

Coaches will contact the PI when situations arise that are not covered in the Anticipated Complaints Guidebook.

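### Adverse-event capture relies on participants volunteering complaints; coaches who already phone weekly are never told to ask, so device-site events are likely to be under-recorded

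*Protocol*

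**What the plan says.** Section 9 (Assessment of Safety) lists three ways in which adverse events will be monitored.

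- **Participant to coordinator.** "Participants in the study will be instructed to call the study doctor's clinical research coordinator to report all AE and SAE", limited to events related to the study devices.
- **Coach.** "Study coaches will listen for any reports of AE or SAE in the course of their communications with participants", after which the coach connects the patient with the coordinator.
- **Manufacturer's support line.** Reports that reach it are documented and passed to the sponsor, and the coordinator then follows up.

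Appendix B, which holds the coaches' questions, opens in the same conditional way: "When patients share a complaint, program coaches will identify the complaint in the Anticipated Complaints Guidebook". Only after that step does the script run: "Based on the complaint type, coaches will then ask questions to determine" severity and relatedness. Section 6, under Integration with patient care, is also conditional: "Should patients mention a potential study-related health concern to their coach".

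Regular contact is already planned. Figure 2 says "Throughout the study, patient will receive a weekly call from patient's coach", and section 7 (Patient Participation) says "Coaches will schedule weekly calls with participating patients". Under Program Length, the weekly calls continue after the 10 weeks of CGM. The content of the calls is described as teaching: "Education will be centered around the four educational objectives", together with standard-of-care messages and a review of how to handle hypoglycemia. No adverse-event question is listed there, and the data-collection table in section 10 has no adverse-event item.

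**The concern.** When events are recorded only if the participant raises them, the count depends on willingness to speak up as well as on what happened. Voluntary reporting can lose events but does not create them, so the likely direction of error is downward.

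This matters here for three reasons. The CGM system is investigational and not FDA-approved (section 3), with a new applicator and a longer-wear sensor than the commercial product (section 6, Program devices). Section 10 says the study is meant to inform a larger one. The formative evaluation is also meant to record difficulties that participants encounter, and a skin reaction or a painful insertion is one of those. A low count from this study could be carried forward as evidence that the sensor is well tolerated when nobody had asked.

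**Working it through.** The protocol states no adverse-event rate, so there is no figure to reproduce. The check is mainly of the text, plus one exposure calculation.

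**1. Who starts each route?**

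| Place in protocol | What starts the process | Is anyone told to ask? |
|---|---|---|
| Section 9, coordinator route | Participant telephones | No |
| Section 9, coach route | Participant reports during a conversation | No |
| Section 9, manufacturer route | Participant contacts the support line | No |
| Section 6, Integration with patient care | Participant mentions a concern | No |
| Appendix B script | Participant shares a complaint | Only after the complaint |
| Section 6, CGM-based education and coaching | Scheduled coaching | No adverse-event item listed |
| Section 10 data table | Scheduled collection | No adverse-event item; exit questionnaire content not given |

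Every route that the protocol labels as adverse-event monitoring starts with the participant.

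**2. How much exposure is covered?** Inputs: 100 participants (section 7), 10 weeks of wear (section 6, Program Length), 10-day sensor life (section 6, Program devices).

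- Sensor wears per participant: 70 days / 10 days = 7.
- All participants: 7 × 100 = 700 sensor wears, or 70 × 100 = 7,000 sensor-days.

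This assumes full enrolment, full wear and full sensor life. Early stopping lowers it; early sensor replacement would raise the number of insertions but not the sensor-days.

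**3. How many chances to ask already exist?** One call a week for 10 weeks is 10 per participant, or 10 × 100 = 1,000 during CGM wear. One further call after wear ends makes 11 × 100 = 1,100. These are scheduled calls; completed calls will be fewer.

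**4. Can the shortfall be sized?** Recorded events = true events × share reported. The protocol gives neither factor, so any count of missed events would be a product of two guesses, and none is offered. The consequence can still be put in general terms. If no participant among 100 had a recorded event, the one-sided 95% upper bound on the true share affected would be 1 − 0.05^(1/100) = 3.0%, provided every affected participant was captured. If only a fraction r is captured, the bound becomes about 3.0% / r. Under voluntary reporting r is unknown, and so is the bound.

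**5. Does timing make it worse?** Section 9 defines itching, redness and inflammation by their state 48 hours after sensor removal, yet no contact is set to ask about that. For most site complaints, Appendix B rates relatedness by whether a sensor was at the location within 2 days or longer ago. If that is judged when the participant calls, a late report can move from possibly related to probably not related. A weekly question shortens the delay, and an onset date allows the 2-day rule to be applied to the event rather than to the call.

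**The case against.** The strongest reply is that the protocol promises no adverse-event rate. Its primary aim is implementation measures, its effectiveness endpoints are glucose, medication and care use, and section 9 describes monitoring and referral in a study the sponsor considers minimal risk. That is correct, and it limits the point: no planned estimate is invalidated. It does not remove the case for asking, because counts from an unapproved device will be read whether or not they are a formal endpoint.

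Second, other sources narrow the gap. Medical records and claims may show events that led to care; a participant who stops syncing is contacted; technical-support requests and an exit interview are collected. None of these is set up to capture adverse events, and mild skin reactions may well appear in none of them.

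Third, the Anticipated Complaints Guidebook, the Appendix C chart, the case report form and the exit questionnaire are not shown, and section 9 cites an Appendix D of coach guidance that is not shown under that label. A standing question in one of them cannot be excluded. This stands as a limit on certainty. Section 9 is nevertheless where the monitoring method is fixed, and it asks coaches only to listen.

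A reader might also infer that a week with no report can never be told from a week when nobody asked. That goes too far: section 10 collects call recordings and the calls attempted and completed, so contact and content could be reconstructed in part, with effort. A reader might further infer that the participants who talk least will look safest. That is plausible, but nothing in the protocol demonstrates it.

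**Conclusion.** The point holds as a likely, unquantified under-recording of device-site events. It rests on the text of section 9 and Appendix B, on the absence of any solicited question in the visible document, and on the general direction of error in voluntary reporting. The exposure concerned is about 700 sensor wears under full participation.

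It is tempting to say that events will be under-counted by some stated proportion. The documents do not support that: they give no true event rate and no reporting rate. Nor do they show that the sponsor's risk classification is wrong; they show only that low counts obtained this way would be weak support for it.

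This is an inexpensive improvement to make. It does not stop the study from running.

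**What to change.** In section 9, and again at the head of Appendix B, require coaches to put one fixed question at each completed weekly call during CGM wear and at the first call after wear ends. For example: *Since our last call, have you had any skin, pain, bleeding or sensor problem where a device was worn?* Log yes or no and, on yes, the onset date, then run the existing Appendix B script. Report event counts together with the number of calls at which the question was asked. A rate per 100 sensor-days is optional. If the Guidebook or another coach document already contains such a question, move it into section 9.

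**Cost.** At an assumed half minute per call, 1,100 calls × 0.5 minutes = 550 minutes, roughly 9 hours of coach time in all, plus fields in the coaching platform for the answer and onset date. Each yes adds time for the script and for the coordinator's assessment. Recorded counts will rise, and the report should say why. No new visit or staff is needed.

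**What it leaves open.** Participants who miss calls remain unasked; the call denominator makes that visible but does not cure it. Weekly calls are not timed to the 48-hour definitions. Separately, section 9 and Appendix B use different pain thresholds (8 or more on the 10-point scale in section 9, against 3 to 5 recorded as mild in Appendix B) and must be reconciled before any count can be interpreted.

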## 8. Treatment of Subjects

This program will provide dedicated resources to assure informed consent.

Patients will be instructed to continue to follow the advice of their physicians, including taking prescribed medications.

Patients will sign and date an IRB-approved consent form that indicates that if they are injured from applying or wearing the CGM system or activity tracker in the course of the program that they will receive treatment and that their insurance may be billed. Copays and costs related to injuries from applying or wearing the CGM devices and activity tracker which are not paid for by patient's insurance will be covered by Savvysherpa (Sponsor). Charges for medical care will be based on insurance contracted rates and not mastercharge sheet prices.

Patients with medical concerns related to the study devices will be instructed to contact the study doctor and/or his staff for evaluation. Patients with any other health will be encouraged to see their providers, or if needed, seek emergency assistance as part of their normal standard of care.

Patients and study staff will be provided with the device manufacturers' technical assistance telephone numbers to report any device-related problems or concerns.

Patients will be provided with a program phone number to call and report other problems or concerns.

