- Any reports of AE or SAE received by Dexcom's Customer Care and Technical Support representatives will be documented and reported to the Sponsor. Coaches will then promptly notify the study doctor's clinical research coordinator of these reports so that the coordinator can then follow up with the patient to assess event severity and relatedness, and schedule the patient for care, if needed.

The Sponsor-Investigator will receive CGM-related AE and SAE information from Dexcom through secure data transfers. AE and SAE information from the study doctor will also be stored and transferred securely. Any other records pertaining to AE and SAE from patient conversations with program staff will be recorded and documented using call-management software and the patient's Case Report Form.

The Sponsor-Investigator will ensure proper reporting of AE and SAE to Chesapeake IRB, the CGM manufacturer, the FDA, and any other regulatory bodies according to regulations and standard operating procedures. (See Appendix C for a chart illustrating the reporting process, and Appendix D for AE assessment guidance for coaches.)

Patients will be provided with a summary printout of their recorded CGM data at the end of their participation with CGM. Patients can share their CGM data with their providers.

The Standard of Care guidelines associated with the program direct patients to seek medical care when needed. Guidance exists within the guidelines to seek medical advice when glucose values are extremely high over long periods of time, fluctuate rapidly from high levels to low levels and vice versa, or a pattern of low glucose values is present. Coaches will remind patients of these guidelines but will not give medical advice. Coaches can send summary CGM data to patients upon patient request.

Because the CGM data is an adjunct to patients' diabetes care, the investigator and research staff will NOT constantly monitor patients' realtime CGM data nor will research staff and coaches contact patients' medical providers on behalf of patients when low or high CGM values are observed. Patients will be responsible for using the blood glucose meter to manage their diabetes and to seek medical attention when needed.

Episodes of hyperglycemia or hypoglycemia that require patients to seek medical attention will be considered an AE or SAE depending upon the situation.

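### Medically attended hypo- or hyperglycemia counts as an adverse event whatever its cause, but participants are told to report device-related events, and no route shown actively asks about glycemic episodes

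*Protocol*

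**What the plan says.** **What counts.** Section 9 ends with the definition: "Episodes of hyperglycemia or hypoglycemia that require patients to seek medical attention will be considered an AE or SAE depending upon the situation". It sets no condition about relation to a device.

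**What participants are told.** Three places bear on this.
- Section 9 has them call the research coordinator "to report all AE and SAE related to the use of the study devices".
- Section 6, under *Integration with patient care*, is limited to CGM: "any health problems associated with the use of their CGM devices, they will be directed to contact the study doctor's CRC".
- Section 8 says "Patients with medical concerns related to the study devices will be instructed to contact the study doctor and/or his staff for evaluation". Its next sentence, which seems to have lost a noun, covers everything else: "Patients with any other health will be encouraged to see their providers", or emergency care if needed. It does not ask that the study be told.

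**What else could pick up an event.** Section 9 adds "Study coaches will listen for any reports of AE or SAE in the course of their communications with participants" and has coaches connect such patients with the coordinator. Coach calls are weekly (Section 7, *Patient Participation*) and continue after CGM ends (Section 6, *Program Length*). Reports to the manufacturer's support line are passed to the sponsor and followed up. The opening of Section 9 sends patients with safety concerns to the study doctor or his staff.

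**The concern.** The definition is wider than the instruction meant to supply the events. Someone treated for a low glucose has little reason to attribute it to a sensor or an activity tracker, so the instruction depends on an attribution that many patients would not make.

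Such episodes are foreseeable on the Protocol's own terms. Coaches review how to deal with hypoglycemic episodes (Section 6, *CGM-based education and coaching*). Figure 1 anticipates both single and sustained hypoglycemia. The Section 10 table tracks basal and bolus insulin, glipizide and glyburide. Yet the device-associated events listed in Section 9 and the risks set out in Section 12 do not include hypo- or hyperglycemia, so participants get little prompt to think of it as reportable.

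The stake is the quality of the adverse event count. Section 10 says the study is to inform a larger one. A low count produced by incomplete ascertainment could be carried into the safety planning of that study.

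**Working it through.** The Protocol states no figure on this point, so there is nothing to reproduce. The check sets each route beside the definition and asks whether it is limited to device events and whether anyone asks about glycemic episodes.

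| Route | Limited to device events? | Asks about glycemic episodes? |
|---|---|---|
| Participant calls coordinator (Section 9) | Yes | No |
| Participant contacts coordinator (Section 6, *Integration with patient care*) | Yes, CGM only | No |
| Participant contacts study doctor (Section 8) | Yes; other matters go to providers or emergency care | No |
| Safety concerns go to study doctor (Section 9, opening) | No | No |
| Coach on weekly call (Sections 7 and 9) | No in Section 9; Section 6 refers to concerns that may be study-related | No; the coach listens |
| Coach question sets (Appendix B, as shown) | Skin, insertion-site and sensor-wire complaints | None shown |
| Manufacturer's support line (Section 9) | No | No |
| Provider review of patient data (Figure 1) | No | Looks at data for possible medication adjustment; not linked to event recording |
| Medical records and care utilization (Section 10) | No | Collected, but not named as a source of adverse events |

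**Case 1: during CGM wear.** A participant is treated in an outside emergency department for a low glucose and does not connect it with the sensor. Section 9 counts the episode. The three participant instructions do not ask for it, and Section 8 has sent the participant where they went. It reaches the study only if the participant mentions it to a coach, the support line or the clinic, or if someone reads the outside record with adverse events in mind. No section assigns that last task.

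**Case 2: after CGM ends.** Transmitters are returned after 10 weeks (Section 6, *Program devices*), while coaching and tracker use run to February 28, 2018. The activity tracker and smartphone are then the main study devices left. A glycemic episode in this period has no CGM to be related to, but the definition still counts it.

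**Size.** Let N be the number enrolled, p the proportion with a medically attended episode and c the fraction captured. The expected number of affected participants recorded is N × p × c. The Protocol gives N = 100 and nothing for p or c. Since c cannot exceed 1, missed episodes can only lower the count, but by how much cannot be calculated.

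**The case against.** The strongest reply is that the participant's call to the coordinator is one route among several, and that the others carry no device limit. Much of this stands.
- Coaches pass on any adverse event they hear of. Their calls are weekly and center on glucose, so a treated low is a likely topic.
- Appendix B covers complaints outside its guidebook: the coach documents what is known and contacts the principal investigator. Only the transfer to the clinic is optional.
- Participants are recruited from the study clinic's own patients, and Figure 1 describes their physician as the study doctor. Many of the providers in Section 8 are therefore the study site.
- Figure 1 has the provider review data that show hypoglycemia. This sits uneasily with the Section 9 statement that staff will not constantly monitor CGM data, but it may bring some episodes to a clinician's notice.

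A reader might infer that adverse event capture as a whole is confined to device events, or that under-counting is certain. The text supports neither. The narrow wording belongs to the participant instructions, which do not forbid other reports. The chart in Appendix C, the coach guidance cited as Appendix D and the full complaints guidebook are not visible, so nothing can be concluded from their silence.

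What the reply does not show is any route that asks. Each one described depends on the participant raising the episode, on a clinician happening to see it, or on a record not designated for this purpose.

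**Conclusion.** The mismatch is real and should be corrected. Medically attended hypo- and hyperglycemia may be under-counted, most plausibly when treated outside the study clinic or after the 10 weeks of CGM. This rests on two assumptions: that some participants will not attribute such an episode to a device, and that the documents not shown contain no active question about it.

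Three stronger readings should be resisted. No numerical estimate of missed events is justified, because any capture fraction would be invented. Calling hypoglycemia the program's main metabolic risk goes beyond the Protocol, which does not rank risks this way. Nor does the Protocol plan a conclusion that the program is safe: this is a formative, exploratory evaluation whose primary aim is implementation, and the Section 10 endpoints include no formal safety endpoint. The consequence is a less reliable adverse event count, not a threat to the primary aim.

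**What to change.** 1. Reconcile the reporting instructions in Section 6 (*Integration with patient care*), Section 8 and Section 9 with the definition at the end of Section 9. Participants should be told to report to the study any hypo- or hyperglycemic episode for which they sought medical attention, wherever it was treated and whether or not they think a device was involved.
2. Add one fixed question on this to the existing weekly coach call, through to the end of the study, with any positive answer going to the coordinator as coaches' reports already do.
3. Name the medical records already collected under Section 10 as a cross-check for these events.

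These changes affect ascertainment only, not clinical care. They use calls and records already planned, and the cost is slightly more adverse event paperwork. Any low-glucose threshold for summarizing CGM data can be left to the analysis plan.
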